## Primary Outcome Analysis

To evaluate changes in researcher-rated PTSD symptom severity over time and treatment differences, a LMM will be fitted using restricted maximum likelihood (REML) estimation. The primary model includes baseline scores as covariate, treatment condition as fixed effect, time as categorical variable, an interaction term between treatment condition and time, and a random intercept for each participant to account for within-subject correlations. An interaction effect between treatment condition and time variables would indicate differential treatment effects over time. To appropriately model the within-subject correlation of repeated outcome measures across unequally spaced timepoints, an unstructured covariance matrix will be applied to the residuals in the LMM. This results in the following model equation:

$$Y_{ij} = \beta_0 + \beta_1 \cdot Baseline_i + \sum_{k=1}^{3} \beta_{2k} \cdot Group_{ik} + \sum_{l=1}^{3} \beta_{3l} \cdot Time_{jl} + \sum_{k=1}^{3} \sum_{l=1}^{3} \beta_{4kl} \cdot (Group_{ik} \times Time_{jl}) + u_i + \varepsilon_{ij}$$

Where:

- *Yii*: Outcome for participant *i* at timepoint *j*
- *Baseline*i: Baseline outcome value for participant *i*
- *Groupik*: Dummy-coded treatment condition indicators (3 dummies: CR, PE, EMDR; WL = reference)
- *Timejl*: Dummy-coded time indicators (3 dummies: midtreatment, posttreatment, 6-month follow-up; baseline = reference)
- $Group_{ik} \times Time_{il}$ : Group-by-time interaction terms
- $u_i$ : Random intercept for participant i
- $\varepsilon_{ii}$ : Residual error
- Fixed effects:
  - Intercept  $\beta_0$ : Mean outcome at baseline for WL
  - $\circ$   $\beta_1$ : Effect of individual baseline outcome value (covariate)
  - $\circ$   $\beta_{2k}$ : Group main effects at baseline, compared to WL
  - $\circ$   $\beta_{3l}$ : Time effects for WL (how outcomes change over time within WL)
  - $\circ$   $\beta_{4kl}$ : Additional group-specific changes over time relative to WL

To quantify the magnitude of treatment effects, effect sizes will be estimated for timepoints T3 and T6 based on the mean pre-post change (i.e. baseline scores vs. follow-up scores) of the treatment condition minus the mean pre-post change of WL, divided by the pooled pretest standard deviation 

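### The primary model uses the baseline score both as a covariate and as an outcome row, so with the unstructured residual matrix it cannot be fitted as written, and its interaction terms are raw change-score differences

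*SAP*

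**What the plan says.** All of the following is in the SAP, Primary Outcome Analysis.

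- Covariate: "The primary model includes baseline scores as covariate". The equation has one term in `Baseline_i`, with a coefficient β1 common to all times.
- Time: "Dummy-coded time indicators (3 dummies: midtreatment, posttreatment, 6-month follow-up; baseline = reference". The sums over time run to 3, so there are four time levels.
- Coefficients: β0 is "Mean outcome at baseline for WL", β2k is "Group main effects at baseline, compared to WL", and β4kl is "Additional group-specific changes over time relative to WL". The text treats a group-by-time interaction as the sign that treatments differ over time.
- Covariance: "an unstructured covariance matrix will be applied to the residuals in the LMM", together with "a random intercept for each participant to account for within-subject correlations". Estimation is by REML.

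The next section, Secondary and Tertiary Outcome Analyses, applies similar methodology to the continuous outcomes and repeats the same right-hand side in the logistic model. It takes therapy-versus-waitlist comparisons at each timepoint from estimated marginal means.

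**The concern.** Either way of using baseline is legitimate alone. One may condition on it as a covariate and model follow-up only, or one may treat it as the first of four outcomes. The printed model does both, so the T0 outcome is regressed on itself.

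Three things follow. The specified model has no REML solution. The terms that the SAP presents as treatment effects gain nothing from the covariate. The stated meanings of β0 and β2k are false: with `Baseline_i` in the model, β0 refers to a waitlist participant with a baseline score of zero, and β2k compares groups at T0 among people with the same T0 score, a difference that is zero by construction.

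The primary estimate would therefore depend on whatever repair is chosen after the fit fails, with unblinded data in hand, and different repairs give different answers.

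**Working it through.** **Inputs.** From the SAP, Sample Size Calculation: two-sided α = 0.05, power 0.80, effect d = 0.5, correlation between repeated measures ρ = 0.45, m = 3 follow-ups, attrition 20%, 50 per arm. Assumptions of this check: equal SD at all visits, and ρ = 0.45 also between baseline and follow-up unless r is varied.

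**1. The plan's sample size.** Two independent means: 2(1.96 + 0.8416)²/0.5² = 62.79 per arm. The factor for the mean of three follow-ups with no baseline term is (1 + 2ρ)/3 = 1.90/3 = 0.633. The product is 39.77, so 40; 40/0.80 = 50. The stated figure reproduces.

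**2. Is T0 really an outcome row?** The printed fixed effects have 1 + 1 + 3 + 3 + 9 = 17 columns. With T0 rows the design has rank 17. Without them it has rank 13, because three time dummies cannot be estimated from three visits that also have an intercept. The printed coding works only with T0 rows.

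**3. No maximum.** At β1 = 1, β0 = 0, β2k = 0, every T0 residual is exactly 0. For 200 simulated participants (4 × 50) with the random-intercept variance at 0, the REML log-likelihood as the T0 residual variance falls is:

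| T0 residual variance | REML log-likelihood | β1 |
|---|---|---|
| 1 | -984 | 0.659 |
| 10⁻² | -558 | 0.992 |
| 10⁻⁴ | -110 | 0.9999 |
| 10⁻⁶ | 339 | 1.000 |
| 10⁻⁸ | 788 | 1.000 |

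In the limit each 100-fold cut adds (200 − 5)/2 × ln 100 = 97.5 × 4.605 = 449, without end. With 10–20% of follow-ups missing, the log-likelihood rose from -861 to 915 over the same range.

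**4. What β4kl estimates.** `Baseline_i` does not vary over time, so it cancels from any within-person change. With complete data, β4kl in one simulated arm was -0.263, -0.474 and -0.543 at every value of the T0 variance, identical to the raw differences in mean change. Follow-up-only analysis of covariance gave -0.213, -0.425 and -0.489. With missing follow-ups, β4kl converges to a change-score model without the covariate.

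**5. Cost in precision.** At a single visit the variance factors are 2(1 − r) for change and 1 − r² for covariance adjustment; their ratio is 2/(1 + r).

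| r | ratio |
|---|---|
| 0.3 | 1.54 |
| 0.45 | 1.38 |
| 0.6 | 1.25 |
| 0.7 | 1.18 |

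For the mean of three follow-ups at 0.45 and 40 evaluable per arm, power is Φ(0.5/√(2f/40) − 1.96):

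| Analysis | factor f | power |
|---|---|---|
| Follow-up only, as in the sample size | 0.633 | 0.80 |
| Change score, 0.633 + 1 − 0.90 | 0.733 | 0.74 |
| Covariance adjustment, 0.633 − 0.2025 | 0.431 | 0.93 |

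A change-score analysis of that average needs 62.79 × 0.733 = 46.05, so 47 evaluable and 47/0.80 = 58.75, so 59 randomised per arm.

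**6. If the analyst drops the unstructured matrix and keeps only the random intercept.** The SAP does not specify this. In 10,000 simulated null trials (40 per arm, ρ = 0.45) with T0 rows, the marginal-mean contrasts against waitlist rejected in 8.0% at T3 and 11.5% for the three-visit average; without T0 rows the rates were 4.8% and 5.1%. A separate run of 40,000 trials gave 7.8% and 11.7% with T0 rows. The T0 rows shrink the random-intercept variance (0.10 instead of 0.25), while the residual variance stays at 0.55. β4kl itself rejected in 5.1%.

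**The case against.** The strongest reply is that the error is one of drafting. The stated model would fail visibly, the SAP (General principles) has an independent statistician consulted throughout, and a competent analyst would drop the T0 rows. That lowers the chance of a wrong published result. It does not remove the defect: the time coding and the definitions of β0 and β2k all point to T0 being an outcome, and the SAP does not say which repair to use.

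A reader might go further than the document allows in four ways.

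- *Every treatment comparison loses its baseline adjustment.* This holds for β4kl, and for the marginal-mean contrasts only in the limit as the T0 variance goes to 0. In the random-intercept fallback those contrasts keep most of it: variance factor 0.816 at T3, against 0.797 for covariance adjustment.
- *The primary test has an inflated false-positive rate.* The inflation arises only under a fallback that the SAP does not specify, and only for the marginal-mean contrasts. The interaction terms stay near 5%.
- *The plan's variance is 70% too large.* The ratio 0.733/0.431 = 1.70 compares with an analysis that the sample size never assumed. Against the planned 0.633 the excess is 16%. The primary analysis text also names no three-visit-average contrast.
- *The sample size is wrong.* It reproduces.

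**Conclusion.** The specification error stands and should be corrected before analysis. As printed, the primary model has no REML solution. This follows from the algebra and does not depend on any assumed correlation, but it does depend on the unstructured matrix, which the SAP specifies. With complete data, β4kl is an unadjusted change-score difference whatever value β1 takes.

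The precision cost depends on a baseline-to-follow-up correlation that the SAP does not state: 18% to 54% more variance than covariance adjustment at a single visit for r between 0.7 and 0.3. If r is 0.45, power for the three-visit average is about 0.74 rather than 0.80. These figures assume equal SDs over time. The false-positive rates of about 8% and 11–12% are a warning about one possible improvised repair and do not describe the planned analysis.

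Separately, a random intercept cannot be distinguished from an unstructured residual matrix, so the model stays over-parameterised even after the T0 rows are removed.

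**What to change.** Preferred: restrict `Y_ij` to T2, T3 and T6 with two time dummies (T2 as reference). Keep `Baseline_i`, condition and condition-by-time (13 parameters, all estimable). Use the unstructured residual matrix and delete the random intercept. Take the therapy-minus-waitlist contrasts from estimated marginal means. Replace the sentence that reads the treatment effect from the interaction, because with T2 as reference the interaction misses an effect that is constant over follow-up.

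Alternative: keep T0 as an outcome row, delete the covariate and the random intercept, and constrain the arm means to be equal at T0.

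In either case, redefine β0, β2k, β3l and β4kl, and carry the correction to the models in Secondary and Tertiary Outcome Analyses. A baseline-by-time term is optional. The planned pre-post effect size may stay.

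Cost: SAP wording and a few lines of R. No new data and no more participants.

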## Secondary and Tertiary Outcome Analyses

For continuous outcomes, LMMs with similar methodology as the primary outcome analysis will be applied. For dichotomous outcomes (e.g., clinician-rated presence of PTSD diagnosis) generalized linear mixed models (GLMMs) with a logit link function will be used, in line with the following model equation:

$$\log\left(\frac{\Pr(Y_{ij}=1)}{1-\Pr(Y_{ij}=1)}\right) = \beta_0 + \beta_1 \cdot Baseline_i + \sum_{k=1}^3 \beta_{2k} \cdot Group_{ik} + \sum_{l=1}^3 \beta_{3l} \cdot Time_{jl} + \sum_{k=1}^3 \sum_{l=1}^3 \beta_{4kl} \cdot (Group_{ik} \times Time_{jl}) + u_i + \varepsilon_{ij}$$

Here, the left-hand side of the model equation indicates the log-odds of the outcome being 1 (e.g., no longer meeting PTSD diagnosis criteria).

The trial protocol specified Generalised Estimating Equations (GEE) would be used to analyse dichotomous outcomes. This plan has been updated to employ GLMMs, as they allow explicit modeling of random effects and individual-level variability, while offering more robust performance when handling missing data under missing at random (MAR) assumptions, which better suits our study's anticipated data structure.

Similar to the primary analysis, effect size of continuous outcomes will be estimated with  $d_{ppc2}$ . For dichotomous outcomes, odds ratios (ORs) will be calculated from the fitted GLMM. Here, exponentiated model coefficients will be interpreted as odds ratios comparing the odds of the outcome between treatment arms and timepoints.

In addition to testing treatment effect on primary and secondary outcomes over time, post-hoc pairwise comparisons between treatment groups and the waitlist control group will be conducted at each timepoint using estimated marginal means with Bonferroni correction to adjust for multiple comparisons.

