# **Study Overview**

## Introduction

This Statistical Analysis Plan (SAP) outlines the statistical methodologies and procedures for analysing data from the RE.PROCESS study, a four-armed randomized controlled trial. Three trauma-focused therapies (Prolonged Exposure [PE], Eye Movement Desensitization and Reprocessing [EMDR], and Cognitive Restructuring [CR]) are compared to a waitlist control group (WL) in individuals with co-occurring posttraumatic stress disorder (PTSD) and lifetime psychotic disorder. Primary and secondary outcomes are measured at baseline (T0), mid-treatment (T2) at 7 weeks, posttreatment (T3) at 3 months, and 6-month follow-up (T6). An extensive study protocol, including information on rationale, participants, and interventions, is published elsewhere.

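### The logistic mixed model for PTSD diagnosis includes baseline rows with no events, so the exponentiated coefficients the SAP names as odds ratios are not interpretable, although the follow-up contrasts with waitlist are

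*SAP*

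**What the plan says.** The SAP's Introduction describes a comparison of three therapies with waitlist (WL) "in individuals with co-occurring posttraumatic stress disorder (PTSD) and lifetime psychotic disorder". PTSD diagnosis on the CAPS-5 is the only dichotomous outcome in Table 1 and belongs to the secondary objective, which asks for effects both over time and at each visit.

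Secondary and Tertiary Outcome Analyses states: "For dichotomous outcomes (e.g., clinician-rated presence of PTSD diagnosis) generalized linear mixed models (GLMMs) with a logit link function will be used". The left-hand side of the equation is "the log-odds of the outcome being 1 (e.g., no longer meeting PTSD diagnosis criteria"). The right-hand side repeats the primary model's equation and gives no new definitions, so those in Primary Outcome Analysis apply:

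- Time has three dummies: "midtreatment, posttreatment, 6-month follow-up; baseline = reference".
- β1 is the "Effect of individual baseline outcome value (covariate").
- β2k are "Group main effects at baseline, compared to WL".

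Odds ratios are then defined: "exponentiated model coefficients will be interpreted as odds ratios comparing the odds of the outcome between treatment arms and timepoints". Separately, post-hoc comparisons of each therapy with WL "will be conducted at each timepoint using estimated marginal means with Bonferroni correction".

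**The concern.** A model built for a continuous score is carried over to a binary outcome whose baseline value is fixed by who was recruited. If everyone has PTSD at T0, the T0 rows contain no events in any arm and the baseline covariate does not vary. The quantities anchored at baseline (intercept, group effects, time effects, interactions) then have no finite or unique estimate, and these are what the SAP says it will exponentiate and report.

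Two planned results for a named secondary outcome are at stake: the coefficient odds ratios with their Wald tests, and the group-by-time test, which Primary Outcome Analysis treats as the sign of a differential effect over time.

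**Working it through.** **Inputs from the SAP.** Four arms of 50; visits T0, T2, T3 and T6; Y = 1 for loss of diagnosis; three group dummies, three time dummies with T0 as reference, nine interactions and a baseline-outcome covariate. The 50 per arm is not in dispute and reproduces: 2 × ((1.960 + 0.842)/0.5)² = 62.79; × (1 + 2 × 0.45)/3 = 39.8, so 40; 40/0.80 = 50.

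**Are T0 rows in the outcome?** Yes. Three follow-up dummies plus an intercept would be collinear if only follow-up rows were used, and the SAP names baseline as the reference level.

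**Rank.** Columns: 1 intercept + 1 baseline + 3 group + 3 time + 9 interactions = 17. With a constant baseline diagnosis the rank is 16, whether it is coded 0 or 1. So β1 is not identified.

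**Algebra with 0/50 events in each arm at T0.**

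- β0 = logit(0), which goes to −∞.
- β3l = finite − logit(0), which goes to +∞.
- β2k = logit(0) − logit(0), undefined.
- β4kl = (finite follow-up difference) − β2k, undefined.
- β2k + β4kl = therapy minus WL at a follow-up visit, finite.

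Coding Y = 1 as presence of PTSD reverses the signs and changes nothing else.

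**Random-intercept logistic fit.** This used one simulated data set and 25-point quadrature, after dropping the aliased covariate. The follow-up rates and the random-intercept SD of 1.5 are assumptions; the separation at T0 does not depend on them. Simulated events out of 50 at T0, T2, T3, T6 were WL 0, 10, 19, 18; CR 0, 17, 24, 23; PE 0, 19, 26, 25; EMDR 0, 11, 24, 22.

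| Maximum iterations | β0 | β3 (T6) | β4 (CR, T6) | exp(β4) | β2 + β4 for CR at T2, T3, T6 |
|---|---|---|---|---|---|
| 20 | −7.43 | 6.68 | 1.19 | 3.3 | 0.877, 0.516, 0.540 |
| 50 | −27.14 | 26.39 | 3.43 | 30.9 | 0.896, 0.535, 0.538 |
| 200 | −31.27 | 30.51 | 3.90 | 49.4 | 0.896, 0.535, 0.538 |

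At 50 iterations the approximate SEs are 56,125 for β0 and 6,424 for the CR-by-T6 term; at 200 no valid SE is returned. The log-likelihood is −374.934 in both.

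**Post-baseline rows only, same data.** CR minus WL is 0.896, 0.535 and 0.538, that is odds ratios of 2.45, 1.71 and 1.71, with log-likelihood −374.934. The T0 rows add nothing on the treatment effect.

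**Fixed-effects logit as a second illustration.** From 10 to 24 iterations the intercept moves from −11.6 (SE 27.9) to −25.6 (SE 30,547), and an interaction SE rises from 39 to 43,200. A T6 therapy-versus-WL contrast stays at 1.206 (SE 0.429) at every iteration count.

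**The group-by-time test.** Leave out the nine interactions. The T0 cells are still fitted perfectly as β0 goes to −∞, so β2k is free to take up any therapy effect common to T2, T3 and T6. At follow-up the full model has 12 free cells and the reduced model 3 time + 3 group = 6 parameters. The test therefore compares 12 − 6 = 6 effective parameters, not the nominal 9, and all six describe departures from a constant effect. With assumed follow-up rates giving a near-constant odds ratio of about 3.4, the interaction likelihood-ratio statistic was 0.01, against 31.3 for a treatment test on the post-baseline rows.

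**The case against.** The strongest reply is that the clinically relevant odds ratios are not lost. The SAP already plans marginal-means comparisons of each therapy with WL at each visit, and at T2, T3 and T6 these equal β2k + β4kl, which the working shows to be stable and identical to a fit without T0 rows. This stands. A reader might infer that no therapy-versus-WL odds ratio can be obtained at any visit; the documents do not support that. What fails is narrower: the raw exponentiated coefficients, their Wald tests, any T0 contrast and the interaction test.

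Second, universal PTSD at T0 is not a stated rule. The SAP lists no eligibility criteria, and the inference rests on the described population and on the outcome being worded as a loss of diagnosis. This also stands, but it softens the result without removing it. If a few participants were below threshold at T0, estimates would be finite but nearly separated and very unstable, and each T0 outcome would equal its own covariate.

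Third, software may drop the aliased covariate and would probably warn of trouble, and the SAP provides for an independent statistician. Dropping the covariate costs no information. It does not repair the separation, and an analyst who adapts the model after seeing the failure is choosing the analysis after the data.

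Finally, the residual term in the logit equation is a slip of notation. Standard software fits no such term, and no result changes.

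**Conclusion.** The defect is real but limited in reach. For PTSD diagnosis, the coefficients that the SAP names as odds ratios are infinite or not identified if all participants have the diagnosis at T0, and highly unstable if nearly all do. The simulated drift from about 3 to about 50 shows that such a figure is arbitrary; it is not an estimate of bias. The over-time test is the more consequential loss, because it runs without error in likelihood-ratio form and still gives almost no signal for a sustained, constant benefit (0.01 against 31.3 in the illustration).

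The follow-up contrasts with WL are sound and already planned, but the SAP lists them as post-hoc comparisons and not as its odds ratios. The sample size and the continuous primary outcome are untouched by this point. The algebra rests on the T0 inference alone; the sizes also rest on assumed follow-up rates.

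**What to change.** In Secondary and Tertiary Outcome Analyses:

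1. Fit the GLMM to T2, T3 and T6 rows only, with two time dummies and a follow-up visit as reference.
2. Drop the baseline-diagnosis covariate, or replace it with the baseline CAPS-5 total score. Either removes the aliasing.
3. Define the reported odds ratios as the therapy-versus-WL contrast at each follow-up visit, with 95% CI, in place of exponentiated raw coefficients.
4. Base the over-time test on the treatment terms jointly (main effect plus interaction) in this post-baseline model.
5. As tidying only, delete the residual term from the logit equation and state the coding of Y as a rule instead of an example.

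The cost is SAP wording and model code. Baseline CAPS-5 is already collected, and leaving out the T0 rows loses no information on treatment (log-likelihood −374.934 with and without them in the simulated data).

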#### Secondary objective

Secondary objectives are to compare the effects of CR, PE, EMDR, to WL for researcherrated severity of PTSD symptoms at the separate time-points (i.e. mid-treatment, posttreatment, and at 6-month follow-up) and to test the effects (over time and at each timepoint) for clinician-rated presence of PTSD diagnosis according to the DSM-5 criteria, and self-reported severity of complex PTSD symptoms.

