## Sample Size Calculation

A formal power analysis was conducted to determine the required sample size for the planned longitudinal intention-to-treat (ITT) analyses using linear mixed models (LMM).

Based on data from previous randomized controlled trials in this field , the calculation used the following parameters: significance level ( $\alpha$ ) of 0.05 (two-sided), power (1- $\beta$ ) of 0.80, expected correlation between repeated measures ( $\rho$ ) of 0.45, and 3 repeated follow-up assessments. The minimum detectable effect size was set at 0.5 (medium effect, compared to waiting list control), while accounting for an anticipated attrition rate of 20%. These calculations indicated that 50 participants would be needed in each study arm. Therefore, our aim will be to randomize a total of 200 participants.

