## **Statistical Methods**

## General principles

This Statistical Analysis Plan describes the methods for analysis of the effect of traumafocused therapies for individuals with PTSD and psychosis on primary, secondary, and adverse outcomes. Other analyses outlined in the published protocol, such as costeffectiveness analysis, will be described and published separately.

All analyses will be completed in R (version 4.4.2) unless stated otherwise. All tests are two-sided and a significance level of  $\alpha$ =0.05 is adopted.

Data will be analysed following the intention-to-treat principle, ensuring all randomized participants are analysed in their assigned groups, regardless of adherence or missing data. Missing data will be treated as missing at random.

Statistical analyses will be carried out by [name], under supervision of dr. [name], dr. [name], dr. [name], and prof. dr. [name]. An independent statistician will be consulted throughout the analysis process.

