# Sensitivity Analyses

To evaluate the robustness of the findings of the primary outcome analysis, the following sensitivity analyses will be performed:

- Per-protocol analysis: estimating treatment effects among participants who completed their allocated therapy (i.e., participants who completed all 16 therapy sessions or participants who met criteria for early completiona).
- Multiple imputation sensitivity analysis: compare primary model with only assessment completers to model with missing outcome data imputed to examine if data is missing at random (MAR). Missing data in the outcome variable will be handled using multiple imputation via chained equations.

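### The PTSD-diagnosis model leaves out the CAPS-5 severity score from the same interviews, which costs precision and can bias the arm contrast if severity-related dropout differs between arms

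*SAP*

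**What the plan says.** The Secondary objective section names "clinician-rated presence of PTSD diagnosis according to the DSM-5 criteria" as a secondary outcome, over time and at each time-point. Table 1 takes both this diagnosis and the primary severity score from the CAPS-5, so a severity score should exist wherever a diagnosis does.

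The section Secondary and Tertiary Outcome Analyses gives the diagnosis model: a logit GLMM with a baseline term, arm, visit, arm by visit and a random intercept. The baseline term is defined under Primary Outcome Analysis as the baseline value of the outcome being modelled, which here is the yes/no diagnosis. The SAP explains the move from GEE partly by the GLMM "offering more robust performance when handling missing data under missing at random (MAR) assumptions".

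General principles says of all analyses: "Missing data will be treated as missing at random". The Sensitivity Analyses section, which contains the multiple imputation, is there to test the "robustness of the findings of the primary outcome analysis". No sensitivity analysis covers the diagnosis outcome.

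**The concern.** Missing at random (MAR) is always relative to what a model conditions on. If dropout depends on the last observed CAPS-5 score, the primary linear mixed model has that score and can allow for it. The diagnosis GLMM has only the earlier yes/no results. A participant just above the diagnostic threshold and one with very severe symptoms look identical to it, although they differ in their chance of losing the diagnosis and perhaps of dropping out. The general MAR statement can therefore hold for the primary outcome and fail for this one.

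The baseline covariate does not repair this. The SAP describes the population as people with PTSD, so baseline diagnosis is nearly constant. If it were fully constant, its coefficient could not be separated from the intercept.

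Two things are at stake for a named secondary outcome: precision that the collected data would give at no cost, and, under some dropout patterns, the estimated contrast of each therapy with waitlist (WL).

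**Working it through.** **1. The plan's own figure.** The Sample Size Calculation section uses two-sided alpha 0.05 and power 0.80, a correlation "of 0.45, and 3 repeated follow-up assessments", and 20% attrition. It adds: "The minimum detectable effect size was set at 0.5".

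n = 2 × (1.960 + 0.842)² / 0.5² × (1 + 2 × 0.45)/3 = 62.8 × 0.633 = 39.8, rounded up to 40. Then 40 / 0.80 = 50 per arm, as stated. This size was set for a continuous outcome. The correlation and attrition are carried forward below.

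**2. Set-up for the diagnosis model.** One therapy arm and WL were simulated.
- From the SAP: correlation 0.45, 50 per arm, overall attrition 20%, effect 0.5 SD.
- Assumed, not in the SAP: everyone diagnosed at baseline; diagnosis is severity plus small noise above a cutoff; the therapy effect on severity is reached at T3 and T6; monotone dropout depends on the last observed severity (log-odds 1 per SD unless stated); the split of dropout by arm; and 0.7 as an upper value for the correlation.

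The planned random-intercept GLMM was fitted to the observed follow-up diagnoses (T2, T3, T6). It was compared with full data and with imputation of diagnosis through CAPS-5 severity.

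**3. Bias (200,000 per arm).** The T6 risk difference is for no longer meeting the diagnosis, therapy minus WL. RD values run full data / planned GLMM / imputation; OR values run full data / planned GLMM.

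| Dropout | RD, corr. 0.45 | OR, corr. 0.45 | RD, corr. 0.7 | OR, corr. 0.7 |
|---|---|---|---|---|
| Random, 20% each | 0.195 / 0.194 / 0.196 | 2.81 / 2.80 | 0.211 / 0.212 / 0.211 | 3.93 / 3.94 |
| More severe leave, 20% each | 0.196 / 0.198 / 0.196 | 2.82 / 2.80 | 0.213 / 0.219 / 0.214 | 3.95 / 3.91 |
| More severe leave, 30% therapy, 10% WL | 0.199 / 0.218 / 0.198 | 2.86 / 3.12 | 0.213 / 0.245 / 0.214 | 3.95 / 4.66 |
| More severe leave therapy, less severe leave WL, 20% each | 0.197 / 0.226 / 0.197 | 2.84 / 3.29 | 0.211 / 0.256 / 0.213 | 3.92 / 5.18 |

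- At 0.45 the bias in the last two rows is 0.218 − 0.199 = 0.019 and 0.226 − 0.197 = 0.029. At 0.7 it is 0.032 and 0.045.
- With slopes up to 2 per SD, the range widened to about 0.02 to 0.05 at 0.45 and 0.03 to 0.08 at 0.7.
- With no true effect, the last two rows give OR 1.09 and 1.15 at 0.45, and 1.17 and 1.32 at 0.7.
- When more severe participants leave equally in both arms, each arm's remission rate is too high by about 1.6 to 2.0 points (0.45) or 2.3 to 2.9 points (0.7), but the contrast hardly moves.
- The severity contrast built from the observed scores stayed at about −0.50 SD throughout, so these patterns are indeed MAR for the primary outcome.

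**4. Precision (50 per arm, 300 simulated trials, random or equal severity-related dropout).** The SD of the T6 risk difference under the planned GLMM is 0.107 to 0.110 at 0.45.
- Imputation through CAPS-5: variance ratio 0.864 and 0.847 at 0.45, 0.850 and 0.830 at 0.7. That is about 14 to 17% lower.
- Imputation plus baseline severity: 0.816 and 0.799 at 0.45 (18 to 20% lower), 0.677 and 0.676 at 0.7 (32% lower).

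Since 1/0.816 = 1.23 and 1/0.799 = 1.25, the gain at 0.45 equals that from roughly 23 to 25% more participants. One variance from 300 trials has a relative Monte Carlo error of √(2/299) = 8%. The ratios come from the same trials and are better determined, but they should be read as rounded.

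**5. Baseline severity alone.** With complete data, 40 against 40, the variance of the T6 risk difference falls by about 9% at correlation 0.45 (power 0.43 to 0.46) and 18% at 0.65 (power 0.47 to 0.56).

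A separate simulation looked at this covariate under dropout. It assumed a 26-point cutoff, 20% dropout, and severity-related dropout in the therapy arm only. The risk difference for having PTSD was −0.210 (SD 0.112) from the GLMM and −0.194 (SD 0.104) with baseline CAPS-5 added, against a true −0.183. So 0.016 of the 0.027 bias was removed, about 59%. The Monte Carlo error of these means is about 0.007, so that share is approximate.

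**The case against.** A single-outcome mixed model under MAR is ordinary practice for a secondary binary endpoint, and so is keeping sensitivity analyses for the primary outcome. Nothing in the SAP contradicts itself here. The bias is small: a shift of 0.025 with a standard error of 0.11 raises a two-sided 5% test only to about 5.6%, before the planned Bonferroni correction. The SAP gives no dropout pattern by arm, so the biased rows in the table rest on assumption. All of this stands, and it limits the point to an improvement.

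Three stronger readings are tempting and are not supported.

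- A reader might infer that severity-related dropout in itself biases the therapy contrast. It does not: with equal dropout in both arms the OR stays at 2.80 against 2.82 (correlation 0.45) and 3.91 against 3.95 (correlation 0.7).
- A reader might infer that the stated MAR advantage over GEE is mistaken. It is a comparison of two methods, and it is fair as such. The GLMM was unbiased when dropout depended on recorded diagnoses (OR 2.85 with full data and 2.85 as planned), and it was nearer the truth than observed proportions whenever dropout depended on history.
- A reader might infer that imputation should replace the GLMM as main analysis, with diagnosis derived from an imputed total score. But the outcome is "clinician-rated presence of PTSD diagnosis according to the DSM-5 criteria", and the SAP gives no total-score cutoff for it. A replacement logistic model without the random intercept would also estimate a different odds ratio from the participant-specific one planned.

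What the objection does not remove is the loss of precision. It needs no assumption about differential dropout, and it arises because a nearly constant covariate stands where an informative one from the same interview is available.

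**Conclusion.** The point holds as a matter of efficiency, and conditionally as a matter of bias. The diagnosis GLMM adjusts for a nearly constant baseline value and leaves out CAPS-5 severity, so it gives up precision under any dropout pattern, including none.

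Bias in the arm contrast arises only if dropout depends on severity beyond diagnosis and does so differently between arms. At the planned correlation it is then mostly about 0.02 to 0.03 on the risk difference, roughly a quarter of a standard error (0.029/0.11 = 0.26). It is larger with a higher correlation or steeper dropout.

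Differential dropout is plausible when participants know their allocation and WL participants receive therapy only after T6, but that is an inference and the SAP does not state it. The sizes rest on the assumed cutoff, dropout slopes and split by arm.

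**What to change.** **Secondary and Tertiary Outcome Analyses.** In the PTSD-diagnosis GLMM, use the baseline CAPS-5 total score in place of, or in addition to, baseline diagnosis. Keep the GLMM as the main analysis, and leave the sentence comparing it with GEE as it is. Note that the reported odds ratio is then also conditional on baseline severity. This is a free improvement: one covariate, already collected.

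**Sensitivity Analyses.** Extend the planned chained-equation imputation to PTSD diagnosis. Impute diagnosis by arm with the CAPS-5 scores at all visits as auxiliary variables, and do not derive it from a total-score cutoff. Then fit the same GLMM and pool the results. This is a cheap improvement: a little more analysis work, with no new data, visits or participants. Its small downside is dependence on an imputation model. That model needs some care with about 50 participants per arm, because score and diagnosis come from the same interview and are closely tied.
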